5.2.1 Rescue Medication

Fluconazole will be used as rescue medication in this investigation, and patients will receive a prescription for fluconazole if considered necessary to relieve their VVC symptoms on Day 14. Patients withdrawing at any point in the investigation may receive fluconazole if considered necessary by the Investigator. The dose of fluconazole will be decided by the Investigator on an individual basis. The use of rescue medication will be recorded in the eCRF.

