5.7 Prior and Concomitant Medication

Information about any concomitant medication, including OTC medications and vitamins taken by patients during the study and within 14 days prior to inclusion shall be documented in the eCRF. The generic name or trade name, dosage, and reason for use shall be recorded for all medications.

NOTE: Antifungal medication during the study and within 14 days prior to inclusion is strictly prohibited

See [Appendix 1, Section 3](#) for specific questions.

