Appendix 1 Patient Questionnaire

Section 1. Vulvovaginal Symptoms

Day(s) 0, 4, 7, 14, and 35; or Day(s) 0, 4, 7, 11, 14, 21 and 42 if receiving prolonged treatment. Questions will be asked by the Investigator at Day(s) 0, 7, and 14 (for patients receiving prolonged treatment); and by the Clinical Trial Unit at remaining days.

Scoring of symptoms

	0 = none (absent)	1 = mild (slight)	2 = moderate (definitely present)	3 = severe (marked, intense)
Irritation				
Itching				
Burning				

The question “Have the symptoms returned, so that you need to seek medical care?” (yes/no) will be asked at Day(s) 14 and 35 if not receiving prolonged treatment and at Day(s) 21 and 42 if receiving prolonged treatment.

Section 2. Usability

Day 7 and Day 14 if receiving prolonged treatment:

Is the vaginal tablet easy to use?

- Yes
- No
- If no, provide reason: _____

Do you find the use of the vaginal tablet gentle?

- Yes
- No
- If no, provide reason: _____

Is the treatment odor free?

- Yes
- No

Is the treatment smear-free and dripless?

- Yes
- No

How do you generally regard the treatment?

1	2	3	4	5	6	7	8	9	10
Not satisfied					Very satisfied				

Section 3. Concomitant Medications

Day(s) 4, 7, 14, and 35; or Days(s) 4, 7, 11, 14, 21, and 42 if receiving prolonged treatment); patients will be asked: “since the last study visit or telephone contact, have you changed dose or taken any new medication?”

Section 4. Adverse Events

The following question will be asked at each patient contact: “since the last visit / telephone contact, have you had any health problems?”

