### 7.2.2 *Per-protocol analysis sets*

Per Protocol (PP) Population 1 (PPAS Clinical Cure) - This will include all FAS patients without any major protocol deviation, i.e. patients who have completed the study and sufficiently complied with the study protocol, have available primary endpoint data and have received the study treatment according to protocol. The final definition of a major protocol deviation will be decided and defined at the clean file meeting and documented in the clean file report. If a relevant number of patients are excluded from the PP population, then the analysis of the primary clinical performance endpoint will be provided for the PP population. The main purpose with this analysis set is to analyse the primary endpoint, i.e. Clinical Cure.

Per Protocol (PP) Population 2 (PPAS Recurrence) - In addition to what was specified in the CIP, a second Per-protocol analysis set will be defined with the main purpose of analysing recurrence. The rationale for this is that the different recurrence rate analyses are regarded as important to also perform using a “per protocol” approach. The main purpose with this per protocol dataset is thus to analyse Recurrence. This population will constitute a sub-population from PP population 1 defined

above, and will be defined in similarity with this population, but instead based on the secondary recurrence rate endpoints. The final definition of a major protocol deviation with respect to these secondary endpoints, will be decided and defined at the clean file meeting and documented in the clean file report.

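### PPAS Recurrence can drop patients because they recurred, so its recurrence rate is liable to be biased low

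*SAP*

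**What the plan says.** **The set.** SAP 7.2.2 creates PPAS Recurrence, which the CIP did not have, because per-protocol recurrence analyses are regarded as important. SAP 7.11 repeats this as a planned change. The set is nested: "This population will constitute a sub-population from PP population 1".

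**Its parent.** PP population 1 is limited to "patients who have completed the study and sufficiently complied with the study protocol, have available primary endpoint data", and to patients treated according to protocol.

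**What is left open.** For the recurrence set, "The final definition of a major protocol deviation with respect to these secondary endpoints, will be decided and defined at the clean file meeting".

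**Antifungals.** Protocol 5.7 states: "Antifungal medication during the study and within 14 days prior to inclusion is strictly prohibited". Protocol 5.2.1 allows two routes to fluconazole. On Day 14, "patients will receive a prescription for fluconazole if considered necessary to relieve their VVC symptoms on Day 14". Otherwise, "Patients withdrawing at any point in the investigation may receive fluconazole if considered necessary by the Investigator".

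**The event.** Protocol Appendix 1, Section 1 asks: "Have the symptoms returned, so that you need to seek medical care". It is asked on Days 14 and 35, or on Days 21 and 42 after prolonged treatment. SAP 8.8 counts a cured patient who answers yes at follow-up as recurred.

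**The main analysis.** SAP 7.9 makes the full analysis set the main set for all clinical performance endpoints.

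**The concern.** A per-protocol set should be defined by things that do not depend on the endpoint it measures. Here the event is worded as a need for care. For a cured patient who relapses, the care the protocol describes is either linked to leaving the study or possibly a breach of it. Both can remove her from the set built to count her event.

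The withdrawal route follows from stated rules. A patient is cured on Day 7, answers yes on Day 14, then withdraws to be treated. Her recurrence is recorded, but she has not completed the study, so she is outside PP population 1. Because PPAS Recurrence is a subset, whatever the clean file meeting decides about deviations for the recurrence endpoints cannot bring her back. The antifungal route is only possible: it depends on how that meeting classifies the use.

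At stake is how the two recurrence rates are read side by side. If the per-protocol rate is close to or below the full-set rate, part of that may come from deleted events rather than from durable cure.

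**Working it through.** The documents give no planning figure for recurrence, so there is none to reproduce. What follows is an illustration.

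**Inputs**
- Patients at risk: 24 planned × 70% assumed cure rate (Protocol 9.3, SAP 5.1) = 16.8, taken as 17.
- Recurrences: 4 of 17 = 23.5%. This is an assumption. It lies near the top of the 13% to 26% relapse range given under Table 1 in Protocol 1.1, which concerns other treatments in severe VVC.
- Interval: two-sided 95% Clopper-Pearson (SAP 7.9.2).
- Shares excluded: assumptions; the documents give none.

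**Step 1. Recurrers excluded, no non-recurrer excluded**

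| Recurrers lost | Rate in the set | 95% CI |
|---|---|---|
| 0 | 4/17 = 23.5% | 6.8% to 49.9% |
| 1 | 3/16 = 18.8% | 4.0% to 45.6% |
| 2 | 2/15 = 13.3% | 1.7% to 40.5% |
| 3 | 1/14 = 7.1% | 0.2% to 33.9% |
| 4 | 0/13 = 0% | 0% to 24.7% |

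The last row is an extreme case.

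**Step 2. When the bias is downward**

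Let R be the true recurrence rate, f the share of recurrers excluded and g the share of non-recurrers excluded. Then

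per-protocol rate = R(1 − f) / [R(1 − f) + (1 − R)(1 − g)].

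If f = g, this equals R. It is below R only if f > g. With R = 20% and f = 50%:
- g = 0: 0.10/0.90 = 11.1%
- g = 25%: 0.10/0.70 = 14.3%
- g = 50%: 0.10/0.50 = 20.0%, no bias
- g = 75%: 0.10/0.30 = 33.3%, biased high

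**Step 3. How many non-recurrers would have to go**

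With 4 recurrers among 17, suppose 2 recurrers are lost. To stay near 23.5%, about half of the 13 non-recurrers must also be lost: losing 6 gives 2/9 = 22.2%, losing 7 gives 2/8 = 25.0%. The balance can also tip the other way. Losing 1 recurrer and 4 non-recurrers gives 3/12 = 25.0%, above 23.5%.

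**Step 4. Which recurrers are exposed**

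The recurrence question is asked twice, and the second time is the last study contact. A patient who first says yes on Day 35 or 42 has reached the end of follow-up, so care sought after that call does not cost her completion. The exposed patients are those who recur and are treated or leave before the last contact.

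**The case against.** **Antifungal use is not automatic exclusion.** A reader might infer that every treated recurrer leaves the set. The documents do not say so. PP population 1 asks for sufficient compliance, no text names antifungal use as a major deviation, and Protocol 5.2.1 itself permits fluconazole on Day 14. This objection stands. Only the withdrawal route follows directly from the written rules.

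**The bias need not be downward.** A reader might infer that the set can only lower the rate. That is wrong: completion and compliance rules also remove non-recurrers, and Step 3 shows a case where the rate rises. This stands too. Downward bias is still the likelier direction. After the cure visit, follow-up is by telephone plus one self-taken swab, and recurrers have a specific reason to leave or to seek treatment.

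**Some of the loss is not specific to this set.** A woman who leaves before she is asked is not a recorded yes in the full analysis set either (SAP 7.1.5, 8.8). That is correct. The loss specific to PPAS Recurrence is clearest for a patient whose yes is on record and who then leaves.

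**The consequence is limited.** The full-set analysis is the main one, the binary secondary endpoints are not tested (SAP 7.9.2), reasons for exclusion go into the clean file report (SAP 7.2), and set sizes are reported (SAP 7.3). Recurrence is not among the withdrawal reasons listed in Protocol 4.5, although that list is open. No text says the per-protocol rate will be used to claim durability. All this limits the weight of the point. It does not justify a set definition that can delete recorded events.

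**Conclusion.** The point holds in a limited form. Through its nesting in a set that requires completion, PPAS Recurrence excludes a cured patient who reports recurrence and then withdraws. It can also exclude one who takes an antifungal, depending on the clean file meeting. The rate is liable to be biased low, on the condition that recurrers are excluded at a higher rate than non-recurrers.

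In the illustration, two lost recurrers move the estimate from 23.5% to 13.3%, about 10 percentage points. The number of recurrences and the shares excluded are assumptions; with equal shares there is no bias. With about 17 patients at risk the intervals are wide in any case, but one or two exclusions visibly change the point estimate.

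The documents do not support saying that the rate must fall, that all treated recurrers are removed, or that the main recurrence analysis is affected.

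**What to change.** In SAP 7.2.2:
- Define PPAS Recurrence by eligibility, treatment received and valid cure status up to the qualifying cure visit (Day 7, or Day 14 after prolonged treatment). Remove the statement that it is a subset of a set requiring study completion.
- State that withdrawal or antifungal use after that visit is not a reason for exclusion, and that a recorded yes stays an event whatever follows.

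Keep the definition of recurrence in SAP 8.8. List antifungal use for VVC after the cure visit beside the rate, or count it as recurrence only in a sensitivity analysis applied equally to the full analysis set. Counting it in this set alone would give the two sets different endpoints. It could also label as recurrent a patient who met the cure threshold (CVVS of 3 or less) with residual symptoms and was treated for those.

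Reconcile Protocol 5.2.1 with 5.7: one permits fluconazole in stated situations, while the other prohibits antifungals during the study without naming an exception.

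The cost is one or two sentences in the SAP, a listing, and the reconciliation of the two protocol sections. No new data are needed. The downside for the sponsor is that the per-protocol recurrence rate may be higher than under the current wording.

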### **7.2.3 Safety analysis set**

The safety analysis set will be based on the same definition as used for FAS. All safety analyses will therefore be performed against the FAS. All patients included in the FAS will be accounted for, including those who did not complete the study along with the reasons for withdrawal.

## **7.3 Disposition of patients**

The following will be presented:

- Number of screened patients, in total.
- Number of screening failures, in total.
- Number of enrolled patients.

Based on the number of enrolled patients, the following will also be presented:

- Number and percentage of patients who did not receive any dose of study treatment.
- Number and percentage of patients who received at least one dose of study treatment.
- Number and percentage of patients who completed the study.
- Number and percentage of patients who withdrew prematurely from the study.
- Number and percentage of patients in each of the analysis sets.

In addition, a frequency table on the primary reason for premature withdrawal from the study will be presented. Percentages for this table will be based on the number of prematurely withdrawn patients.

The number of patients attending each study visit will also be summarised.

## **7.4 Protocol deviations**

Protocol deviations will be presented in a data listing.

The number and percentage of enrolled patients with at least one major protocol deviation leading to exclusion from an analysis set will be presented.

## **7.5 Demographics and baseline characteristics**

Summary statistics and frequencies on demographic data (age) and baseline characteristics (pregnancy test, and diagnosis information) will be presented for all analysis sets.

## 7.6 *Medical history and concurrent diseases*

Medical history and concurrent diseases will be coded according to the Medical Dictionary for Regulatory Activities (MedDRA, version 22.0).

For each system organ class and preferred term, the number and percentage of patients with at least one condition in that system organ class or preferred term will be presented. Medical history and concurrent diseases will be presented in separate tables, based on the full analysis set.

Medical history is defined as events stopped prior to baseline. Concurrent diseases are defined as ongoing events and events stopped on or after baseline. If the start and/or stop date is partially unknown, the following imputation rules will be used for the purpose of classifying the events:

	Imputed start date	Imputed end date
Unknown year	Missing	Missing
Unknown month	1 January	31 December
Unknown day	First of month	Last of month

If it is not possible to classify the condition based on the reported and/or imputed start and end dates, it will be considered as concurrent. In data listings, the dates will be presented as reported.

## 7.7 *Prior and concomitant medication*

Medications will be coded according to the World Health Organisation (WHO) Drug Dictionary, ATC/DD Index 2018, and summarised by therapeutic subgroup (ATC level 2) and preferred name.

For each therapeutic subgroup and preferred name, the number and percentage of patients who used at least one medication of that therapeutic subgroup or preferred name will be presented. Prior and concomitant medications will be summarised in separate tables, based on the full analysis set.

If a reported medication cannot be coded with a preferred name, the lowest available higher-level dictionary term will be used instead in the summary tables. If a medication cannot be coded on a lower level than the therapeutic subgroup or the anatomical main group (ATC level 1), that medication will be presented as 'Not codable' under that therapeutic subgroup/anatomical main group.

Prior medication is defined as medication stopped prior to baseline. Concomitant medication is defined as ongoing medication or medication stopped on or after baseline. If the start and/or stop date is partially unknown, the following imputation rules will be used for the purpose of classifying the medication:

	Imputed start date	Imputed end date
Unknown year	Missing	Missing
Unknown month	1 January	31 December
Unknown day	First of month	Last of month

If it is not possible to classify a medication based on the reported and/or imputed start and end dates, it will be considered as concomitant. In data listings, the dates will be presented as reported.

Any use of rescue mediation (fluconazole) will be identified as any concomitant medication used with "Indication (reason for medication)" equal to "Rescue medication" as recorded in the CRF.

## 7.8 Compliance

Patients will be asked about investigational product administration by telephone on Day 4 and at the site on Day 7, and also on Day(s) 11 (telephone) and 14 (site) if receiving prolonged treatment. No other measurements of treatment compliance will be made. These compliance data will be summarised for the full analysis set. The rate of compliance is defined as the actual amount of study treatment taken divided by the expected amount of study treatment to be taken. The expected amount is based on the planned duration of treatment (*i.e.* for prematurely withdrawn patients, the expected amount is computed as if the patient had not withdrawn). The expected amount is 4 doses for patients without prolonged treatment and 8 doses for patients with prolonged treatment.

## 7.9 Primary and secondary endpoints analyses

All analyses of clinical performance endpoints will be performed on the full analysis set, and these analyses will be considered as the main analyses. If a relevant number of patients are excluded from the PP population, the per-protocol analysis set will be used for supportive clinical performance sensitivity analysis of the primary clinical performance endpoint.

If the stated assumptions that the statistical evaluation is built upon can be questioned, suitable alternative methods may be applied. For example, a 95% confidence interval based on a non-parametric method may be applied if assumption of data belonging to the normal distribution seems not to hold.

All study endpoints (primary, secondary, and exploratory), as well as the related variables specified in the list below in [Section 7.9.2](#), will be presented descriptively.

### 7.9.1 Primary endpoints

- Clinical performance endpoint: Clinical cure rate on Day 7 will be calculated and presented together with a one-sided 95 % confidence interval based on the exact binomial distribution (Clopper-Pearson).
- Clinical safety endpoint: Safety and tolerability will be assessed according to [Section 7.10.2](#).

The primary clinical performance endpoint is the Clinical cure rate on Day 7, where clinical cure is defined as the absence of signs and symptoms of VVC in terms of having a composite vulvovaginal signs-and-symptoms (CVVS) score equal to or below 3, see [Section 3.1.1](#) above. The primary performance objective of the trial is to show that the Clinical cure rate is above 40 %, *i.e.* to show that the lower limit of the one-sided 95 % CI for the observed cure rate is above 40 %.

#### Hypotheses for the primary clinical performance endpoint

Null hypothesis: Clinical cure rate is less than or equal to 40 %.

Alternative hypothesis (one-sided): Clinical cure rate is above 40 %.

The primary clinical safety endpoint, *i.e.* safety and tolerability based on reported treatment-emergent AEs, will be analysed descriptively only, see [Section 7.10.2](#) below, and will thus not be connected to any formal hypothesis testing.

### 7.9.2 Secondary endpoints

The secondary clinical performance endpoints are either binary or continuous.

The usability data, as measured by the patient questionnaire and which contain both binary and continuous endpoints, will only be presented descriptively.

The other binary secondary clinical performance endpoints will be calculated and presented together with a two-sided 95 % confidence interval based on the exact binomial distribution (Clopper-Pearson). No hypothesis testing will be made on the binary endpoints.

The remaining clinical performance endpoints that are considered as continuous endpoints are the change in the CVVS score and the change in the sum of 3 vulvovaginal symptoms scores (itching, burning, and irritation). Here, applying Student's t distribution, a two-sided 95% confidence intervals for the arithmetic mean will be presented. For illustration purposes, the statistical hypotheses for the former endpoint are specified below:

#### Hypothesis for the continuous secondary clinical performance endpoint "Change in the CVVS score"

Null hypothesis: Change from baseline is = 0.

Alternative hypothesis (two-sided): Change from baseline  $\neq$  0.

Below follows a list of all secondary endpoints followed by information on which are binary and which are continuous. Note that, as described in [Section 3.2.1](#) above, the analyses of the secondary endpoints will be performed on 3 different patient categories. These are denoted as A, B, and C below.

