Table 1 Severe Vulvovaginal Candidiasis, Treatment Cure Rates

	Terconazole	Clotrimazole	Fluconazole
Clinical Cure Rate			
7-14 days after treatment	81%	89%	76%-89%
30-35 days after treatment	60%	72%	56%-78%
Mycological Cure rate			
7-14 days after treatment	79%	78%	71%-74%
30-35 days after treatment	62%	54%	53%-56%

Relapse rates after 30 to 35 days were between 13%-26%, see^{33,34} for details.

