3.5.9 Day 14 (\pm 2 Days); Follow-up Telephone Contact

Applicable to patients NOT receiving prolonged treatment

Patients not receiving additional doses of investigational product on Day 7 will be contacted by the Clinical Trial Unit by telephone on Day 14. Patients will be asked questions from the patient questionnaire about VVC symptoms (itching, burning, or irritation), recurrence, concomitant medications, and AEs, if any.

Procedures performed:

- Vulvovaginal candidiasis recurrence
- Symptoms (itching, burning, or irritation) of VVC evaluated by patients according to the scoring scale
- Recording of:
 - concomitant medications, and
 - adverse events

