5 TREATMENTS

5.1 Investigational Product

The investigational product, Gedea Pessary (commercial name *p*Hyph), is a GDL-and-NaG containing pessary to be administered vaginally with a CE-marked vaginal tablet applicator (Schägner GmbH, Steinmauern, Germany). The device is intended to treat vaginal Candida infections, see [Figure 2](#) and [Figure 3](#) for product image and applicator label. Gedea Pessary is a Class IIa medical device according to MDD 93/42/EEC (the Swedish regulation SFS 1993:584 and LVFS 2003:11).

NOTE: The terms investigational product, Gedea Pessary, investigational device, pessary, and vaginal pessary are used interchangeably in the CIP

Gedea Pessary is a white, convex, bullet-shaped tablet, approximately 2 cm in length, contract-manufactured by Galenica AB (Malmö, Sweden). The pessary is slow-release formulated, administering 300 mg GDL and 367.5 mg NaG over 45 hours. Each patient will administer a total of 4 pessaries in the study or 8 if receiving prolonged treatment. The investigational products will be packed in blister packs containing 4 pessaries labeled with *Gedea Pessary* and batch number. Blisters will be packed together with 4 vaginal tablet applicators in a cardboard-box labeled with *Gedea Pessary, for investigational use only*, production date, and expiry date ([Figure 4](#)).

It is the responsibility of the Investigator to ensure that the investigational products are stored in their original packaging in a secure location with access only by authorized personnel, separate from other medications. The investigational product shall be stored at room temperature (15°C -25°C), protected from direct sunlight or freezing. The investigational products *must not* be used outside of the study. For further reference, refer to the IB.

Instructions for use will be distributed at the first visit, advising patients on how to use the product together with the applicator. Briefly, patients will be instructed to: wash their hands and vaginal area prior to use; place a tablet into the applicator and insert as far into the vagina

as is comfortable (without forcing), or until half of the applicator is inside; discard the applicator after use; not use tampons or other vaginal products while using this product.

[figure not shown]
Figure 2 Gedea Pessary and Applicator

Figure 3 Vaginal Tablet Applicator Label

Figure 4 Investigational Product Label

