### 5.1 *Sample size*

Assuming the true cure rate is equal to 70 %, 22 patients are needed to obtain 90 % chance (90 % power) to show that the one-sided 95 % CI for the observed cure rate is above 40 %. To compensate for a small number of non-evaluable patients, 24 patients will be included.

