#### B. For patients not receiving prolonged treatment

- vii] Recurrence rate on Day 14 and Day 35, defined as the proportion of patients clinically cured on Day 7 and thereafter responding "yes" to a yes/no question from the patient questionnaire on whether the symptoms have recurred

The endpoint vii] constitute binary variables.

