#### C. For patients receiving prolonged treatment

- viii] Clinical cure rate on Day 14, defined as the absence of signs and symptoms of VVC in terms of having a CVVS score equal to or below 3

- ix] Proportion of patients having a reduction in CVVS score on Day 14 compared to Day 0
- x] Change in the CVVS score from Day 0 to Day 14
- xi] Proportion of patients having a reduction in the sum of the 3 vulvovaginal symptoms scores (itching, burning, and irritation) on Day 11, Day 14, Day 21, and Day 42, compared to Day 0
- xii] Change in the sum of the 3 vulvovaginal symptoms scores (itching, burning, and irritation) from Day 0 to Day 11, Day 14, Day 21, and Day 42
- xiii] Recurrence rate on Day 21, and Day 42, defined as the proportion of patients clinically cured on Day 14 and thereafter responding “yes” to a yes/no question from the patient questionnaire on whether the symptoms have recurred
- xiv] Proportion of patients receiving prescription for fluconazole on Day 14

The endpoints viii], ix], xi], xiii], and xiv] are binary variables.

The endpoints x] and xii] are considered as continuous variables.

In connection to the endpoints described above, the underlying variables listed below not constituting endpoints (denoted as “other related variables” in the CIP), will be presented descriptively.

- CVVS score (can take integer values in the interval 0-18)
- Vulvovaginal signs: erythema (can take integer values in the interval 0-3)
- Vulvovaginal signs: edema (can take integer values in the interval 0-3)
- Vulvovaginal signs: excoriation (can take integer values in the interval 0-3)
- Sum of all vulvovaginal signs score (can take integer values in the interval 0-9)
- Vulvovaginal symptoms: itching (can take integer values in the interval 0-3)
- Vulvovaginal symptoms: burning (can take integer values in the interval 0-3)
- Vulvovaginal symptoms: irritation (can take integer values in the interval 0-3)
- Sum of all vulvovaginal symptoms score (can take integer values in the interval 0-9)

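### No clinical-performance endpoint after Day 7 covers all treated patients, so the plan contains no estimate of how many are cured and stay well after treatment

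*SAP*

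**What the plan says.** SAP 7.9.2 says that "the analyses of the secondary endpoints will be performed on 3 different patient categories".

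- **A, all patients:** reduction and change in CVVS at Day 7, reduction and change in the symptom sum at Days 4 and 7, the proportion given prolonged treatment, and usability. Nothing on performance after Day 7.
- **B, no prolonged treatment:** one endpoint, "Recurrence rate on Day 14 and Day 35, defined as the proportion of patients clinically cured on Day 7 and thereafter responding" yes to the recurrence question.
- **C, prolonged treatment:** "Clinical cure rate on Day 14, defined as the absence of signs and symptoms of VVC in terms of having a CVVS score" of 3 or less; CVVS change to Day 14; symptom-sum change to Days 11, 14, 21 and 42; recurrence on Days 21 and 42 among those cured on Day 14; fluconazole prescription.

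SAP 7.2.1 splits the full analysis set (FAS) to match. Under SAP 4 and CIP 3.1, patients not cured at Day 7 receive prolonged treatment. Nothing in SAP 7.9.4, 7.11 or 8 brings the two groups back together.

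On data collection, CIP 3.5.9 lists for the Day 14 call to patients without prolonged treatment: "Symptoms (itching, burning, or irritation) of VVC evaluated by patients according to the scoring scale". The same scores and the recurrence question are taken at Day 35 (CIP 3.5.12), and at Days 21 and 42 after prolonged treatment (CIP 3.5.11 and 3.5.13). Signs are examined only on Days 0 and 7, and on Day 14 if treatment is prolonged (CIP 6.1.1).

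CIP 5.1 describes the pessary as "administering 300 mg GDL and 367.5 mg NaG over 45 hours". The first course ends on Day 6 and the second on Day 13.

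**The concern.** The primary cure rate is read close to the last dose, and the plan then follows everyone for about a month. Readers will want to know what share of treated women are cured and stay well once the product has stopped. The planned follow-up results have outcome-selected denominators: recurrence among Day 7 cures in one group, and cure, symptom change and recurrence after a second course in the other. None is a proportion of all patients treated. No rule says how a missed call or fluconazole use counts towards such a proportion. In category B the symptom scores after Day 7 are collected but feed no endpoint.

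The background figures in CIP 1.1 are mostly post-treatment; Table 1, for example, gives rates at 7–14 and at "30-35 days after treatment". A Day 7 rate reported alone invites a comparison that its timing does not support.

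**Working it through.** **1. The plan's own figure.** SAP 5.1: "Assuming the true cure rate is equal to 70 %, 22 patients are needed to obtain 90 % chance (90 % power"), against 40%, one-sided 5%. By the normal approximation, N = ((1.645 × √(0.40 × 0.60) + 1.282 × √(0.70 × 0.30)) / (0.70 − 0.40))² ≈ 21.6, so 22. The figure reproduces. (Under the exact rule of SAP 7.9.1, 24 patients need at least 15 cures and power is 84.7%. That is a separate matter, and nothing below depends on it.) With the planned 24 patients, 70% is 16.8, so about 17 are cured on Day 7 and 7 are not.

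**2. Time since last dose.**

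| Reading | One course (last dose Day 6) | Two courses (last dose Day 13) |
|---|---|---|
| CVVS cure | Day 7: 1 day | Day 14: 1 day |
| First call with recurrence question | Day 14: 8 days | Day 21: 8 days |
| Last call | Day 35: 29 days | Day 42: 29 days |

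One day is inside the 45-hour release. With the +2-day window the cure visit can fall 3 days (72 hours) after the dose, which is outside it. The calls line up at 8 and 29 days on both paths. Calendar Day 14 does not: it is 8 days after the last dose on one path and 1 day on the other.

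**3. What one headline can hide.** Take 17/24 cured on Day 7: 71%, exact two-sided 95% CI 49–87%.

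| Course of events | Well off treatment | Exact 95% CI |
|---|---|---|
| 4 of 17 recur, none of 7 cured | 13/24 = 54% | 33–74% |
| 2 of 17 recur, all 7 cured and stay well | 22/24 = 92% | 73–99% |

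The counts 2 and 4 approximate the 13% to 26% relapse quoted under CIP Table 1 (17 × 0.13 = 2.2; 17 × 0.26 = 4.4). The conditional results are imprecise: 4/17 recurring has CI 7–50%, and 4/7 cured on Day 14 has CI 18–90%.

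**4. General form.** Let c7 be the Day 7 cure rate, c14 the Day 14 cure rate among the rest, and r the recurrence rate, assumed equal after either course. The share well 29 days after the last dose is p = (1 − r) × (c7 + (1 − c7) × c14). The documents give no c14, so 0% to 70% is assumed. With c7 = 70%:

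- r = 26%, c14 = 0: p = 0.74 × 0.70 = 51.8%.
- r = 13%, c14 = 70%: p = 0.87 × (0.70 + 0.30 × 0.70) = 79.2%.

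p equals the 70% headline when c14 = c7 × r / ((1 − r)(1 − c7)). That is 0.091/0.261 = 35% at r = 13%, and 0.182/0.222 = 82% at r = 26%. Below that c14 the all-patient figure is lower than the headline; above it, higher.

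**5. Gaps in the counting rules.**

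- SAP 8.8 defines recurrence only from Day 7 cure; SAP 7.9.2 C uses Day 14 cure.
- Prolonged treatment goes to patients not cured in SAP 4 and CIP 3.1, but to patients whose symptoms persist in CIP 3.5.5. A CVVS of 3 or less allows a residual symptom, so a Day 7 cure could fall in group C.
- SAP 7.1.1 keeps patients with missing data in default denominators, and SAP 7.1.5 imputes nothing. An unanswered recurrence call could therefore act as no recurrence.
- No rule covers fluconazole users at Days 21 and 42.

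**The case against.** The case for leaving the plan alone has substance. This is a 24-patient feasibility study whose primary analysis is fully specified and unaffected. Recurrence is planned on both paths. The safety co-primary covers the whole FAS throughout follow-up. SAP 7.9.2 also lists the symptom items and their sum for descriptive presentation, without restricting that to group C. All of this stands. It narrows the gap to a missing pre-specified estimate with its interval and counting rules.

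A reader might infer four stronger things that the documents do not support:

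- **The conditional results cannot be combined.** They can: the groups are disjoint, counts and patient listings are planned, and the illustrations above do it. What is absent is a rule fixed in advance.
- **The Day 7 rate overstates lasting cure by 9 to 18 points.** That follows only for sustained cure after one course (0.70 × 0.87 = 60.9% and 0.70 × 0.74 = 51.8%, against 70%), where every second-course success counts as a failure. The relapse range also comes from severe VVC under other drugs. The recurrence question here asks about symptoms needing medical care (CIP Appendix 1), so it may capture fewer events.
- **The trial is compared with Table 1.** No such comparison is planned. CIP 3.2 cites a lack of proper comparators, and the test is against a fixed 40%.
- **Every Day 7 reading is on-product.** This holds only nominally, because of the visit window.

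**Conclusion.** The point holds in this form: after Day 7, every clinical-performance endpoint is confined to a group defined by prolonged treatment, and no all-patient estimate of sustained cure is planned although most of the data for one are collected. At 17/24 cured on Day 7, the illustrated off-treatment result runs from 54% to 92% of all patients. In the general form, with c7 at 70%, it runs from 51.8% to 79.2%. These figures assume that the quoted 13% to 26% relapse applies here and after either course, and that c14 lies between 0% and 70%. The direction relative to the headline is undetermined.

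An all-patient endpoint would rest on symptoms and reported recurrence. It cannot be an off-treatment CVVS cure rate, because signs are not examined after Day 7 (or Day 14 if prolonged). This is a worthwhile, inexpensive addition; it does not undermine the primary test.

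**What to change.** Add to SAP 7.9.2 category A and to SAP 8, with the FAS as denominator; give the two proportions in (1) and (2) exact two-sided 95% intervals:

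1. **Sustained cure after one course**, at Days 14 and 35: CVVS of 3 or less on Day 7, no prolonged treatment, no antifungal use, and the recurrence question answered no at each contact up to that day.
2. **Sustained cure after up to two courses**, at 8 and 29 days after the last dose (Days 14 and 35, or Days 21 and 42 if prolonged): cured at the end of the last course, no antifungal use, and recurrence answered no at each contact.
3. **Reduction and change in the symptom sum for all patients**, at the same 8 and 29 days after the last dose and not at calendar Day 14.

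In (1) and (2), count a missing contact as not sustained, and give an observed-data version as a sensitivity analysis.

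In SAP 8.8, base recurrence on Day 14 cure for prolonged-treatment patients, to match SAP 7.9.2 C. The trigger for prolonged treatment in CIP 3.5.5 must be reconciled with that in SAP 4 and CIP 3.1; which applies is for the sponsor to settle. State that the new endpoints rest on symptoms and reported recurrence, and that the Day 7 rate should not be read against post-treatment background rates.

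The cost is a few derived variables from data already collected, some SAP wording, and an entry in SAP 7.11. No visit, sample or dose changes. The downside for the sponsor is a second cure figure, possibly lower, next to the primary one.
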